The primary endpoints of occurrence of DLTs as well as the secondary endpoint of occurrence, severity and duration of treatment-emergent adverse events (TEAEs) and treatment-related AEs according to National Cancer Institute-Common Terminology Criteria for Adverse Events (NCI-CTCAE) v 5.0 are standard objective measures of safety. A 3-week (Part A) and 4-week (Part B) period has been defined as the DLT assessment period to monitor DLT over 42 doses of M3814 and 2 administrations of avelumab for Part A and 10 administrations of M3814 and 8 fractions of RT (3 Gy each) and 3 administrations of avelumab for Part B. Secondary endpoints relating to PK, immunogenicity, and confirmed objective response as assessed by the Investigator using RECIST v1.1 criteria are also standard measurements. Duration of response, PFS and OS will also be determined as secondary endpoints and will serve to assess whether the objective response is associated with lasting clinical and survival benefit.

Part FE:

The primary endpoint is to evaluate the FE (fasted/fed state) on PK of M3814. A 3-week period has been defined as the FE Assessment Period to monitor the exposure both after single and repeated administration of M3814 over 42 doses of M3814 and 2 administrations of avelumab. Secondary endpoints relating to the effects of prandial state on the safety profile of M3814 along with immunogenicity and confirmed objective response as assessed by the Investigator using RECIST v 1.1 criteria are also standard measurements. Duration of response, PFS, and OS will

also be determined as secondary endpoints and will serve to assess whether the objective response is associated with lasting clinical and survival benefit.

Part A, Part B, and Part FE:

The exploratory pharmacodynamic assessments were selected based on the known mechanism of action and effects of M3814 and are relevant to the response, safety, or resistance to the combination. These assessments will contribute to the understanding of AEs and help in the determination of the RP2D.

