In vitro studies suggest that CYP3A, CYP2C9, and CYP2C19 are involved in the metabolism of M3814. Using physiologically based PK modeling and simulation, potent inhibitors and inducers of CYP3A, CYP2C9, and CYP2C19 are predicted to have an influence on the PK of M3814. Therefore, foods (e.g. grapefruit and Seville oranges) or concomitant medications that are potent inducers or inhibitors of these enzymes should be used with caution. Participants will be instructed to avoid any intake of grapefruit, grapefruit juice, Seville oranges, Seville orange marmalade, or other products containing grapefruit or Seville oranges within 7 days before the first administration of the study intervention and during the study intervention administration.

The effect of M3814 on CYP3A-metabolized substrates is complex due to the time dependent inhibition and induction. It cannot be excluded that at high concentrations, M3814 affects the PK

of sensitive CYP3A substrates; therefore, sensitive CYP3A substrates with a narrow therapeutic index should also be used with caution and avoided if possible, during treatment with M3814. Drugs mainly metabolized by CYP2C9 with a narrow therapeutic index are to be used with caution and if possible, avoided during treatment with M3814.

The solubility of M3814 is pH dependent; therefore, antacid drugs and proton pump inhibitors might affect absorption (Section 6.5).

Drugs which are substrates of P-glycoprotein (P-gp) (e.g. dabigatran etexilate, digoxin), breast cancer resistance protein (BCRP) (e.g. rosuvastatin, sulfasalazine), or organic cation transporter 1 (OCT1) (e.g. metformin) with a narrow therapeutic index are to be used with caution. The Investigator may decide not to include a participant in the study, if the participant cannot be withdrawn from the drugs that have a narrow therapeutic index and that are known to be substrates of P-gp, BCRP, or OCT1; if the Investigator decides to enroll a participant who is treated with a drug that is known to be substrate of P-gp, BCRP, or OCT1 and has a narrow therapeutic range, close safety monitoring is advised.

The study will be performed in a study unit with direct access to a Hospital Emergency Unit. Equipment and medications, such as epinephrine and prednisolone equivalents, will be available at the study site for the treatment of emergencies.

Radiotherapy

Refer to Appendix 8 for details of RT.

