Any PK concentrations or PK parameters excluded from summary statistics will be included in subject listings and flagged; a reason for exclusion will be detailed in the CSR (e.g. a footnote or a table of exclusions). Any flags should be included in the study specific SDTM and ADaM data sets.

The following PK parameters will be reported for M3814 and 0-demethylated product M467 (if available) on Day 1 (D1), Day 15 (D15), and Day 22 (D22) and in Part A and Part FE where data permit. Appropriate adjustments will be made for differences in molecular weight (MW) (M3814 MW = 481.92 gmol; 0-demethylated product M467 MW = 467.12 gmol). Concentration results collected on Day 22, Day 29 (Part A), and EoT will be summarized descriptively.

Cmax Maximum observed concentration.

Cmax/Dose The dose-normalized maximum observed concentration (Part A only). Normalized

using the actual dose, and the formula Cmax/Dose.

Ctrough The concentration observed immediately before next dosing on D15, D22, and D29,

(D29 is Part A only).

Ctrough/Dose The dose-normalized trough concentration. Normalized using the actual dose, and

the formula Ctrough /Dose on D15, D22, and D29, (D29 is Part A only).

AUC0-6 Area under the concentration-time curve (AUC) from time zero to time 6 hours

postdose. AUC0-6 will be based on the estimated concentration at 6 hours and not

the concentration at the actual observation time.

AUC0-6/Dose The dose-normalized AUC from time zero to 6 hours postdose (Part A only).

Normalized using the actual dose, using the formula AUC0-6/Dose.

AUC0-12 AUC from time zero to time 12 hours postdose. AUC0-12,D1 will be based on the

estimated concentration at 12 hours after dosing. AUC0-12,D15 from zero to 12 hours postdose with predose D15 concentration used for estimated concentration at

12 hours (Part A only).

AUC0-12/Dose The dose-normalized AUC0-12 (Part A only). Normalized using the actual dose,

using the formula AUC0-12/Dose.

tmax Time to reach the maximum observed concentration Cmax.

Racc(Cmax) Accumulation ratio for Cmax, calculated as Cmax,D15/Cmax,D1 (Part A only).

Frel(Cmax) Relative bioavailability of Cmax of fed (D22) compared to fasted (D15)

Cmax,fed/Cmax,fasted and Cmax of fed (D1) compared to fasted (D15) Cmax,fed/Cmax,fasted

(Part FE only).

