Racc(AUC0-12) Accumulation ratio for AUC0-12 calculated as AUC0-12,D15/AUC0-12,D1 (Part A only).

Frel(AUC0-6) Relative bioavailability for AUC0-6 of fed (D22) compared to fasted (D15)

AUC0-6,fed/ AUC0-6,fasted and as sensitivity analysis AUC0-6 of fed (D1) compared to

fasted (D15) AUC0-6,fed/ AUC0-6,fasted (Part FE only).

λz Terminal first order elimination rate constant.

t½ Apparent terminal half-life,  $t_{\frac{1}{2}} = \ln 2/\lambda_z$ .

The following PK parameters will be reported for M3814 on Day 1 (FD1) and Day 12 (FD10) in Part B where data permit. Concentration results collected on Day 2 (FD2), Day 8 (FD6), and EoT will be summarized descriptively.

Cmax Maximum observed concentration

Cmax/Dose The dose-normalized maximum observed concentration. Normalized using the

actual dose, and the formula Cmax/Dose.

Ctrough The concentration observed immediately before next dosing on FD10 only.

Ctrough/Dose The dose-normalized trough concentration. Normalized using the actual dose, and

the formula Ctrough/Dose on FD10 only.

AUC0-6 Area under the concentration-time curve (AUC) from time zero to time 6 hours

postdose. AUC0-6 will be based on the estimated concentration at 6 hours and not

the concentration at the actual observation time.

AUC0-6/Dose The dose-normalized AUC from time zero to 6 hours postdose. Normalized using

the actual dose, using the formula AUC0-6/Dose.

AUC0-24 Area under the concentration-time curve (AUC) from time zero to time 24 hours

postdose. AUC0-24,FD1 will be based on the estimated concentration at 24 hours after dosing and not the concentration at the actual observation time. AUC0-24,FD10 from zero to 24 hours postdose with predose FD10 concentration used for estimated

concentration at 24 hours.

[figure not shown]
AUC0-24/Dose The dose-normalized AUC from time zero to 24 hours postdose for FD1 and FD10.

Normalized using the actual dose, using the formula AUC0-24,FD1/Dose and

AUC0-24,FD10/Dose.

tmax Time to reach the maximum observed concentration Cmax

Racc(Cmax) Accumulation ratio for Cmax, calculated as Cmax, FD10/Cmax, FD1

The following PK parameters will be reported for avelumab where data permit.

CEOI Concentration observed at the end of infusion period.

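### SAP 16.1: the Part FE Day 1/Day 15 Cmax ratio is labelled relative bioavailability, but it equals the food effect divided by accumulation

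*SAP*

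**What the plan says.** Part FE has one fixed order: a high-fat meal on Day 1, fasting on Day 15 and a high-fat meal on Day 22. M3814 is taken twice daily throughout (Protocol 6.6.5.3; SAP 16.1, Table 11 footnote).

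SAP 16.1 defines Frel(Cmax) first as the ratio "of fed (D22) compared to fasted (D15") and then adds a second ratio of the same kind: "Cmax,fed/Cmax,fasted and Cmax of fed (D1) compared to fasted (D15) Cmax,fed/Cmax,fasted". Nothing ranks the two. For AUC0-6 the wording differs, and the Day 1 version is marked as secondary: "AUC0-6,fed/ AUC0-6,fasted and as sensitivity analysis AUC0-6 of fed (D1) compared to" fasted Day 15.

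In the same list, the Part A accumulation ratios are "Racc(Cmax) Accumulation ratio for Cmax, calculated as Cmax,D15/Cmax,D1 (Part A only") and "Racc(AUC0-12) Accumulation ratio for AUC0-12 calculated as AUC0-12,D15/AUC0-12,D1 (Part A only").

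The SAP plans no predose correction of the Day 15 profile and no adjustment of Day 1/Day 15 for accumulation. It also plans paired fed/fasted plots of Cmax and AUC0-6 for both pairs of days. Protocol 4.2 treats the two situations as distinct, since the assessment period is meant to "monitor the exposure both after single and repeated administration of M3814 over 42 doses of M3814 and 2 administrations of avelumab".

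**The concern.** The Day 1 and Day 15 profiles differ in two respects: food, and whether earlier doses are still on board. Part A uses Day 15/Day 1 to measure the second. Part FE inverts that contrast and calls it relative bioavailability.

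Cmax is a primary Part FE endpoint (Protocol 3.3). Results from Part FE are reviewed for their effect on M3814 dosing recommendations (Protocol 6.6.2). With 6 to 12 participants and two unranked Cmax ratios, a reader could be given two food-effect figures that differ for a reason unrelated to food. A genuine increase with food could also be hidden in the second ratio.

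**Working it through.** **Inputs from the documents.** The dosing interval is 12 h (twice daily). Scheduled doses before the morning dose are 14 × 2 = 28 on Day 15 and 21 × 2 = 42 on Day 22. Part FE post-dose sampling (SAP Table 11) is at 1, 2, 4 and 6 h on Day 1; 1, 2, 3, 4 and 6 h on Day 15; and 2, 4 and 6 h on Day 22, each with a predose sample. The plan states no half-life and no expected ratio, so there is no figure of its own to reproduce.

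**Step 1, algebra.** Insert the unobserved fasted Day 1 value:

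Cmax,D1,fed / Cmax,D15,fasted = (Cmax,D1,fed / Cmax,D1,fasted) × (Cmax,D1,fasted / Cmax,D15,fasted) = food effect / Racc

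With no food effect this is 1/Racc. The identity is for Cmax. For AUC it is only approximate, because Part A accumulation uses AUC0-12 and Part FE uses AUC0-6.

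**Step 2, simple size check.** With linear kinetics, Racc ≈ 1/(1 − 2^(−12/half-life)).
- 3 h: 1/(1 − 0.0625) = 1.067, so the ratio with no food effect is 0.94.
- 6 h: 1/(1 − 0.25) = 1.333, ratio 0.75.
- 8 h: 1/(1 − 0.354) = 1.547, ratio 0.65.

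**Step 3, model.** One-compartment oral model, superposition of earlier doses, no food effect. Half-life and absorption rate (ka) are assumptions: ka 0.7–1.5 per h, except in the 2 h row, where ka is 1 per h. Cmax is taken on the planned sampling times and AUC0-6 on the full curve.

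| Assumed half-life | Cmax, D1/D15 | Cmax shortfall | AUC0-6, D1/D15 |
|---|---|---|---|
| 2 h | 0.98 | about 2% | 0.97 |
| 3 h | 0.90–0.93 | 7–10% | 0.89–0.92 |
| 4 h | 0.82–0.87 | 13–18% | 0.81–0.85 |
| 6 h | 0.69–0.74 | 26–31% | 0.67–0.72 |
| 8 h | 0.60–0.63 | 37–40% | 0.56–0.61 |

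**Step 4, masking.** At a 6 h half-life, a true 1.4-fold increase in Cmax would read 1.4 × 0.69 = 0.97 to 1.4 × 0.74 = 1.04, that is, no effect. In general, a true 25% increase reads 1.25/1.1 = 1.14 at Racc 1.1, 1.25/1.25 = 1.00 at Racc 1.25 and 1.25/1.5 = 0.83 at Racc 1.5.

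**Step 5, direction.** Carry-over can only lower the ratio. Clearance may also change with time: Protocol 6.8 lists CYP3A among the enzymes that metabolise M3814 and says "The effect of M3814 on CYP3A-metabolized substrates is complex due to the time dependent inhibition and induction". If Day 15 exposure fell so that Racc were 0.8, the ratio with no food effect would be 1/0.8 = 1.25.

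**Step 6, the other contrast.** On Day 22 and Day 15 the participant is under repeated dosing, so accumulation cancels and the true ratio with no food effect is 1.00. The sampling times differ, however. On the planned times, with the linear-log trapezoid, half-life 2–12 h and ka 0.5–2 per h, the same model gives Day 22/Day 15 of 0.84–1.00 for Cmax and 0.83–0.99 for AUC0-6. That shortfall comes from the missing 1 h and 3 h samples on Day 22. On predose, 2, 4 and 6 h for both days, the ratio returns to 1.00.

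**The case against.** The strongest reply is that the main contrast is sound. Day 22/Day 15 is listed first for both parameters, and for AUC0-6 the Day 1 ratio is already called a sensitivity analysis. No hypothesis is tested (Protocol 9.1), and no threshold on Frel triggers a decision. Readers will also see Day 15 and Day 22 troughs, separate single-dose and multiple-dose listings and overlaid profiles. Food may be tested as a covariate in a population model if the data suffice. All of this stands, and it limits the consequence. It does not make the label on the second Cmax ratio correct.

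A second reply is that accumulation may be trivial. At a half-life near 2 h it would be, and there the sampling mismatch in Day 22/Day 15 is the larger problem: AUC0-6 0.85–0.92, against 0.95–0.97 for Day 1/Day 15 (planned times, ka 0.7–1.5 per h). Day 1/Day 15 becomes clearly the worse of the two only from about 4 h upward. The SAP does not say accumulation is negligible, and it plans to measure it in Part A.

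A reader might go further and infer that the whole Part FE food-effect assessment is invalid, or that it will show a negative food effect. The documents support neither. One of the two Cmax ratios and one AUC0-6 sensitivity ratio are affected, and the net direction is open because clearance may change with time.

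**Conclusion.** The point holds for the label on the Day 1/Day 15 Cmax ratio. By the SAP's own definitions that ratio is the food effect divided by accumulation, and reporting it as an unqualified relative bioavailability would give a misleading figure on a primary Part FE endpoint. The AUC0-6 version has the same confounding but is already marked as a sensitivity analysis.

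The algebra needs no assumption. The size does: a one-compartment model, linear kinetics and a half-life that the documents do not give. The Cmax shortfall from carry-over could be about 2% or about 40% over the half-lives of 2 to 8 h considered here, and time-dependent clearance could offset or reverse it. The point should be settled before database lock, but it does not undermine Day 22/Day 15 as the food-effect contrast.

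**What to change.** In SAP 16.1:

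1. Name Day 22/Day 15 as the food-effect estimate for both Cmax and AUC0-6, computed on the times common to both days (predose, 2, 4 and 6 h).
2. Remove Day 1/Day 15 from Frel and from the paired fed/fasted plots. Alternatively, keep it for both parameters only as a sensitivity output labelled *food effect combined with accumulation*, shown beside the Part A Day 15/Day 1 ratio at the same dose.
3. Do not present a numerical correction of Day 1/Day 15 as formal. Two are tempting, and both are fragile:
   - Subtracting the decaying predose concentration needs a terminal rate constant from a 6 h profile. The SAP asks for at least three points, excluding tmax, over at least two half-lives. Points at 3, 4 and 6 h span 3 h, which meets the rule only up to a half-life of 1.5 h; adding the 2 h point raises this to 2 h.
   - Multiplying by the Part A ratio uses different, few participants (4 assessed at 100 mg BID, Protocol 4.2). The fasting rules also differ: at least 1 h before and after the dose in Part A, against at least 8 h before and 4 h after on Part FE Day 15 (Protocol 6.6.5.1 and 6.6.5.3).

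The cost is a wording change and a restricted derivation; no new data or samples are needed. The plan loses one unqualified ratio and some Day 15 sampling detail. A common grid without a 1 h sample can miss an early peak on either day, so the full Day 15 profile should still be listed.

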8.5 Pharmacokinetics

The following PK parameters will be calculated, when appropriate, for M3814 and avelumab, where data permit:

Symbol	Definition
AUC _{0-t}	AUC from time of dosing to the time of the last observation
AUC _{0-∞}	AUC from time of dosing to infinity
C _{max}	Maximum serum (avelumab) / plasma (M3814) concentration observed postdose
C _{min}	Minimum serum (avelumab) / plasma (M3814) concentration observed postdose
Cavg	Average serum (avelumab) / plasma (M3814) concentration observed postdose
t _{max}	Time to maximum concentration observed postdose
t _{1/2}	Apparent elimination half-life
Λz	Terminal rate constant
CL/f	Oral clearance
Vz/f	Apparent volume of distribution during terminal phase
Racc[AUC]	Accumulation ratio for AUC
Racc[Cmax]	Accumulation ratio for C _{max}
Fluctuation index	Fluctuation between maximum and minimum concentrations
Frei, Fed/Fasted	Relative bioavailability of M3814 after a breakfast versus after an overnight fast (only for Part FE)

- Whole blood samples of approximately 2.0 mL will be collected for measurement of plasma concentrations of M3814, as specified in the Schedule of Activities (Section 1.3). The actual date and time (24-hour clock time) of each sample will be recorded.
- The quantification of M3814 in plasma will be performed using a validated liquid chromatography/mass spectrometry assay. Concentrations will be used to evaluate the PK of M3814.
- Whole blood samples of approximately 3.5 mL will be collected for measurement of serum concentrations of avelumab, as specified in the Schedule of Activities (Section 1.3). The actual date and time (24-hour clock time) of each sample will be recorded.
- The quantification of avelumab in serum will be performed using a validated immunoassay.
 Concentrations will be used to evaluate the PK of avelumab.
- Remaining samples collected for analysis of avelumab serum concentration may also be used
 to evaluate immunogenicity and safety or efficacy aspects related to concerns arising during or
 after the study.
- Details on processes for collection and shipment of these samples are in the Laboratory Manual.
 The Sponsor will store the samples in a secure storage space with adequate measures to protect
 confidentiality. Retention time and possible analyses of samples after the end of study are
 specified in the respective ICF.
- These samples may also be used for evaluations of metabolites of M3814, for further evaluation

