\* For M3814, only applies if M3814 treatment is stopped. For avelumab if prior to Week 49.

Table 12: Pharmacokinetic Sampling Times for Part B

Week (Day)	Time (h)	M3814	Avelumab
Week 1 (Day 1; FD1)	Predose	х	X
	1	Х	
	Eol		X
	2	X	
	4	X	
	6	X	
Week 1 (Day 2; FD2)	Predose	X	
	2	X	
Week 2 (Day 8; FD6)	Predose	X	
	2	X	
Week 2 (Day 12; FD10)	Predose	X	
	2	X	
	4	X	
	6	X	
Week 3 (Day 15)	Predose		X
Week 5 (Day 29)	Predose		X
	Eol		X
Week 9 (Day 57)	Predose		X
Week 13 (Day 85)	Predose		Х
Weeks 25, 37, 49	Predose		X
EoT*		X	X
30-day Safety FU			X

M3814 will be administered once a day. RT will be given at the dose of 3 Gy per day. M3814 and RT will both be given starting Day 1 for 5 days/week for 2 weeks, at which point both M3814 and RT are discontinued. Avelumab (1 hour infusion) will be administered once every two weeks, starting on Day 1 until PD or unacceptable toxicity. EoI = end of infusion; EoT = end of treatment; FD = fraction day; FU = follow-up.

\* For avelumab, if prior to Week 49.

Table 13: Acceptable Pharmacokinetic Window for Avelumab

Sampling Time	Time From Scheduled Sampling Allowed
Before Bol	Within 120 minutes prior to dose
Eol	Within 15 minutes before Eol

Bol = beginning of infusion; Eol = end of infusion

Table 14: Acceptable Pharmacokinetic Window for M3814

Sampling Time	Time From Scheduled Sampling Allowed	
Predose	Within 60 minutes prior to dose administration	
0.5 to 2 hours postdose	± 20 minutes	
> 2 hours postdose	± 30 minutes	

Samples that are collected outside the specified time windows will be included in the PK parameter estimation (NCA) but will be excluded from the concentration summary and mean concentration plots.

PK concentrations which are erroneous due to a protocol violation (as defined in the CSP), sampling processing or analytical error (as documented in the bioanalytical report) may be excluded from the PK analysis if agreed by the Sponsor. In this case the rationale for exclusion must be provided in the Clinical Study Report (CSR). Any other PK concentrations that appear implausible to the Clinical Pharmacologist/Clinical PK/PD Scientist will not be excluded from the analysis. Any implausible data will be documented in the Clinical Study Report (CSR).

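### The Part B accumulation ratio for M3814 compares a Cmax sampled at 2, 4 and 6 h with one sampled at 1, 2, 4 and 6 h, so it can understate accumulation if peaks are early

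*SAP*

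**What the plan says.** SAP Section 16.1 introduces the Part B parameters with "The following PK parameters will be reported for M3814 on Day 1 (FD1) and Day 12 (FD10) in Part B where data permit". It defines Cmax as the maximum observed concentration, and Protocol Section 8.5 likewise uses the maximum "concentration observed postdose". Nothing is interpolated, so Cmax depends on when blood is drawn. The accumulation ratio is then "Accumulation ratio for Cmax, calculated as Cmax, FD10/Cmax, FD1".

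The M3814 sampling times in SAP Table 12, which agree with Protocol Table 6, are:

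| Row | Predose | 1 h | 2 h | 4 h | 6 h |
|---|---|---|---|---|---|
| "Week 1 (Day 1; FD1") | yes | yes | yes | yes | yes |
| "Week 2 (Day 12; FD10") | yes | no | yes | yes | yes |

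The SAP gives no common-grid rule, sensitivity analysis or caveat for the ratio. The corresponding Part A parameter is "Accumulation ratio for Cmax, calculated as Cmax,D15/Cmax,D1 (Part A only"), and SAP Table 11 samples Part A at 1, 2, 3, 4 and 6 h on both of those days.

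**The concern.** A ratio of two observed maxima measures accumulation only if each maximum had the same chance of catching the peak. Here the numerator has one opportunity fewer, and it is the earliest one. An early peak can be recorded on FD1 and missed on FD10, which lowers the ratio with no change in exposure.

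Racc[Cmax] is a stated secondary PK endpoint for Part B (Protocol Table 9), and SAP Section 7 does not drop it. It is also the only M3814 accumulation ratio in the SAP's Part B list. Part A has an AUC-based ratio as well, so there a distorted Cmax ratio would at least have a companion to be checked against. Protocol Section 6.8 says that CYP3A is involved in M3814 metabolism and that the effect of M3814 on CYP3A substrates includes time-dependent inhibition and induction. A low ratio could therefore be misread as a drug effect, and modest real accumulation could be read as none.

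**Working it through.** The plan states no numerical value for this ratio, so there is no figure to reproduce.

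**Inputs from the documents.** The two sampling grids above; the ratio definition; dosing ("M3814 and RT will both be given starting Day 1 for 5 days/week for 2 weeks", so ten once-daily doses, on Days 1-5 and 8-12); and the sampling window of ±20 min for "0.5 to 2 hours postdose" (SAP Table 14). **Assumed, because the visible text does not give them:** M3814 tmax, half-life and variability.

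**Step 1: direction.** On any day, max(C2, C4, C6) ≤ max(C1, C2, C4, C6). The planned numerator can equal the matched-grid numerator but cannot exceed it, and the denominator is the same. This needs no model.

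**Step 2: can the windows close the gap?** The earliest in-window postdose sample on FD10 is at 2 h − 20 min = 1 h 40 min. Protocol Table 6 gives ±10 min, hence 1 h 50 min. Neither reaches 1 h.

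**Step 3: who is affected?** Participants with C(1 h) > C(2 h). For a one-compartment oral model after a single dose, C(t) is proportional to exp(−ke·t) − exp(−ka·t). Setting C(1) = C(2) gives exp(−ke) + exp(−ka) = 1. At half-life 6 h, ke = ln 2/6 = 0.1155, so exp(−ke) = 0.891, exp(−ka) = 0.109 and ka = 2.215. Then tmax = ln(ka/ke)/(ka − ke) = 1.41 h. At half-lives of 2, 3 and 12 h the boundary is 1.44, 1.43 and 1.39 h. A participant who peaks at 1.5-2 h has the maximum at 2 h on both days and is essentially unaffected.

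**Step 4: size without variability.** Same model, unchanged kinetics, tmax 1 h, ten doses, concentrations in arbitrary units:

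| Half-life | FD1 at 1 h | FD1 at 2 h | FD10 at 1 h (not sampled) | FD10 at 2 h | Planned ratio | Matched 1, 2, 4, 6 h | Common 2, 4, 6 h | True peak ratio |
|---|---|---|---|---|---|---|---|---|
| 3 h | 0.794 | 0.684 | 0.797 | 0.687 | 0.687/0.794 = 0.865 | 1.004 | 1.004 | 1.004 |
| 6 h | 0.891 | 0.820 | 0.952 | 0.874 | 0.874/0.891 = 0.981 | 1.069 | 1.067 | 1.069 |
| 12 h | 0.944 | 0.903 | 1.262 | 1.203 | 1.203/0.944 = 1.274 | 1.337 | 1.332 | 1.337 |

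The shortfall against the matched grid is 13.8%, 8.2% and 4.7%. At tmax 0.5 h it is 5.6-20.5%, at 1.25 h 2.9-6.2%, and from 1.5 h on about 0%.

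**Step 5: size with variability.** Two simulations with different assumptions, both reporting geometric mean ratios:

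- Simulation 1: no true accumulation, 20,000 participants per scenario, half-life 2-6 h, log-SD 0.4 on ka, 0.2 on ke and 0.2 on the occasion scale. The shortfall is 1 minus the ratio.
- Simulation 2: ten doses, 100,000 participants per scenario, half-life 3-12 h, log-SD 0.5 between participants and 0.4 between occasions on ka, 0.4 on ke, residual 0.2. The shortfall is against the matched grid.

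| Typical tmax | Simulation 1: planned ratio (shortfall) | Simulation 2: shortfall |
|---|---|---|
| 0.75 h | 0.75-0.90 (10-25%) | not run |
| 1 h | 0.82-0.93 (7-18%) | 7.9-17.3% |
| 1.5 h | 0.95-0.98 (2-5%) | 6.2-10.9% |
| 2 h | 0.99-1.00 (0-1%) | 4.5-6.3% |
| 3 h | 1.00 (0%) | 1.9-2.4% |

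On the common 2, 4, 6 h grid, simulation 1 returns 1.00 throughout. In simulation 2 the common-grid ratio is within about 0.01 of the matched-grid ratio in every scenario. The shortfall at typical tmax of 1.5 h or later comes from the assumed spread, which places some participants' peaks before 1.4 h.

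**The case against.** The strongest reply is that the mismatch may not matter. If M3814 usually peaks at 2 h or later, the loss is a few percent at most, and the visible documents do not say where it peaks. That stands: it limits the size, though not the direction.

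The second reply is that other planned outputs expose the problem. SAP Section 16.1 reports tmax on both days, summarizes concentrations by day and scheduled time, and overlays all days per dose level in the mean plots. A careful reader could compare the days at 2, 4 and 6 h directly. This also stands as mitigation, but none of it changes the ratio that goes into the table. Protocol Table 6 allows sampling times to be modified, yet a later change cannot supply a 1 h sample for participants already studied. The same table moves sampling to Day 11 (FD9) when Day 12 is a Friday, and adds no 1 h sample there.

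The third reply is that little rests on the number. Protocol Section 9.1 tests no hypothesis, and no escalation rule uses this ratio. This is correct and sets the severity.

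A reader might infer more than the documents support:

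- **That any peak before 2 h biases the ratio.** Only C(1 h) > C(2 h) does, which means a peak before about 1.4 h in the model used.
- **That the ratio is pushed below 1.** At half-life 12 h and tmax 1 h it is 1.274 against a true 1.337: too low, but still showing accumulation.
- **That the planned ratio can never exceed the true peak ratio.** The bound is against the matched-grid ratio. At half-life 12 h and tmax 3 h the planned and matched ratios are both 1.359 against a true 1.355, because no discrete grid catches the peak exactly.

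**Conclusion.** The concern holds in a conditional form. The grid mismatch is a fact of both documents, and its one-sided direction follows from taking a maximum over a subset of times. The size is not known. On the assumed one-compartment kinetics and variability, the understatement is roughly 5-25% if typical tmax is about 1 h or earlier, up to about 11% at 1.5 h, up to about 6% at 2 h and about 0-2% at 3 h. Those figures rest on assumed half-lives of 2-12 h and on the variability listed above, and different values would move them.

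Part A is not affected. The documents do not support a claim that the reported Part B ratio will be materially wrong, or that any dosing decision depends on it. The parameter is secondary and descriptive, so the correction is worthwhile but not essential.

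**What to change.** In SAP Section 16.1, for Part B, compute the accumulation ratio as the maximum over the nominal 2, 4 and 6 h samples on FD10 divided by the maximum over the same nominal times on FD1. Label it a common-time accumulation ratio, so that it is not taken for a ratio of full-grid peaks. Keep the full-grid FD1 Cmax as a separate parameter. If the planned ratio is also shown, add a footnote stating that FD10 has no 1 h sample.

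The cost is one or two sentences and one derived variable. It needs no new blood draw, and it applies to participants already sampled. The drawback is a coarser grid: if M3814 peaks near 1 h, the common-time ratio compares post-peak concentrations on both days and leaves a valid FD1 observation out of the ratio. Adding a 1 h sample on FD10 would match the grids and avoid that, but only through a change to the sampling schedule and only for future participants.
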